2.0 STUDY OBJECTIVE

The purpose of the study is to determine the efficacy/durability, the safety, and the feasibility of iTBS in 5 adolescents with MDD.

Specific Aims.

Aim 1. Investigate the efficacy and durability of effects by estimating the magnitudes of pre-regimen vs. post-regimen longitudinal changes in CDRS-R, HAM-D, and NSSIB evaluations.

Hypothesis 1: Adolescents with MDD will show improvement in symptoms over 20 iTBS sessions as measured by the Children's Depression Rating Scale Revised (CDRS-R), HAM-D and NSSIB measures.

Hypothesis 2: Adolescents with MDD will show reduction of depressive symptoms will persists through the 12 week follow up period of the study.

Hypothesis 3: Adolescents with MDD who demonstrate NSSIB at the start of the trial will show reduction in NSSIB after iTBS treatments.

Aim 2. Investigate safety of the treatment regimen by assessing suicidality with the Columbia Suicide Severity Rating Scale (C-SSRS).

Hypothesis 1: Adolescents with MDD will show reduction in suicidal thoughts and behavior with iTBS treatment as measured by the Columbia Suicide Severity Rating Scale (C-SSRS) and a psychiatrist's clinical assessment.

Aim 3. Investigate treatment feasibility by assessing treatment completion and withdrawal.

Hypothesis 1: iTBS will be considered feasible if: a.) 15/20 (75%) iTBS treatment sessions are completed by all subjects, and; b.) no more than one of five subjects (20%) withdraw from iTBS due to intolerable side effects or persistent symptoms of MDD.

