3.0 INVESTIGATIONAL PLAN (brief overview)

3.1 Study Design

Type of design: A pilot study that is an open label, feasibility study. This study will aim to reduce depressive symptoms in adolescents using iTBS and evaluating the safety of methods. This will be an uncontrolled study design.

The study phases are described below:

- **Screening/Baseline:** This will include informed consent, an Intake Assessment (including psychological assessments / questionnaires), medical review with physical exam, vitals, UDS, and pregnancy screening for a total of about 2 hours, and needed collateral. Screening will last up to 1 week prior to scheduling first treatment session in order to allow sufficient time to gather all needed medical information. The entire screening visit itself should last up to 3 hours with patient and caregiver.
- **Intervention/Treatment:** Participants will receive iTBS immediately following screening, should they be determined eligible. Treatment visits will last 20 days, Monday-Friday for approximately 10 minutes each session. Although the actual procedure takes 3 minutes, we estimate close to 5-7 minutes will be required for setting up the treatment and the equipment. Treatment will occur over a 4-week period. Once per week, additional cognitive and safety assessments will be performed. During the last the day of the treatment phase, efficacy and safety scales will be performed also. Subjects will continue to receive routine psychiatric care from their outpatient mental health team, which may consist of a psychiatrist and a therapist.

- **Follow up:** There will be 3 follow up appointments to evaluate long-term efficacy and safety at 1 week, 4 weeks, and 12 weeks since the last treatment session.
- **Unscheduled Visits:** These will be done for any safety concerns and may include any of the assessments listed above. If pregnancy is suspected, another urine pregnancy test will be performed.

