3.4 Study Population

Inclusion Criteria:

- A score of greater than 40 on the CDRS-R and 17 on HAM-D.
- Documentation of DSM-V criteria for current MDD or TRD will be required for study entry.
- Patients may be on antidepressant medication at a stable dose or receiving psychotherapy with a licensed provider during the active phase of TMS treatment for 4 weeks.
- Ability to provide consent and take part in questionnaires and scales (i.e.: not currently intellectually disabled).
- The presence of suicidality or NSSIB are not required to enter this study. Although our secondary endpoints include suicidality, and we are also exploring NSSIB, and thus this may not lead to many data, the investigators' plan is to use data from this study to justify a larger study where this can be more robustly investigated.

Exclusionary criteria:

- Past or current diagnosis of bipolar disorder, psychosis, seizures or traumatic brain injury.
- Presence of intracranial metallic implants or fragments, which is a contraindication for TMS.

- Lifetime history of (or currently present) epilepsy.
- Current diagnosis of substance abuse, eating disorder, PTSD (Post Traumatic Stress Disorder), or intellectual disability.* Nicotine use disorder will not directly preclude a potential subject from this study. Although chronic nicotine use does effect central nervous system excitability, [23] what would be more confounding to our study would be if there is a sudden change in nicotine use during the treatment phase, as this may affect the motor threshold. Inclusion will however be at the PI's discretion.
- Current imminent suicide ideation or other clinical reasons for inpatient psychiatric hospitalization.
- Currently pregnant. There is currently not adequate data from this population to ensure safety with the scope of this protocol.
- Any reason the investigator determines may cause noncompliance with study rules or is unfit for receiving treatment.
- Currently taking certain medications including antidepressants, stimulants, benzodiazepines, and antipsychotics, antiepileptic (see Appendix A).
- Any positive drug testing from a urine drug test unless medically indicated with a valid prescription.

*Those with marijuana/cannabis positive results may retest later if at that time they do not meet criteria for substance abuse at screening and agree to refrain from use for the duration of study participation. Decision to be made by Investigator discretion.

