5.2 Efficacy Evaluation

Children’s Depression Rating Scale Revised (CDRS-R) – This is one of the most commonly used assessment tools for pediatrics when identifying depression. It assesses symptom severity and can be administered filtered or unfiltered (in context of mood disorder or not). [28] It is a semi structured interview scale. 17 items are scored, with 3 of these 17 being made from observation versus verbal response [28]. This will evaluate overall wellness to determine efficacy of treatment, measuring sleep, appetite, socialization, school/work functioning, and overall wellness. This is a scaled and scored assessment and is filtered.

Hamilton Depression Rating Scale (HAM-D) – This is the most widely used tool to evaluate depression. Interrater reliability is high at 0.97-0.98. It is easily administered and measures severity of depression. It is considered the “gold standard” when assessing depression. There are 21 items to score however only the first 17 are actually totaled, each question has a scaled answer. [29] The HAM-D used in this protocol is the same tool used for routine clinical services in the Department of Psychiatry at UNC. This will also evaluate overall wellness to determine efficacy of treatment, measuring sleep, appetite, socialization, school/work functioning, and overall wellness. This is a scaled and scored assessment.

SITBI (Self-Injurious Thoughts and Behaviors Interview) short form & semi structured interview – Self-injurious thoughts and behaviors, lifetime and past month will be assessed using the Self-Injurious Thoughts and Behaviors Interview (SITBI) short form, a clinician-administered interview (3-10 min) that assesses the presence, frequency, severity, age-of-onset, and other characteristics of a broad range of self-injurious thoughts and behaviors. The SITBI has strong convergent validity, inter-rater reliability ($K = .90$), and test-retest reliability ($K = .70$). [30] It is a comprehensive assessment that is recommended for use in clinical and research settings. [30] This is a descriptive, yes/no assessment.

Other: Patient/Caregiver Satisfaction questionnaire: This is an original, brief questionnaire using scaled and open ended questions that is self-reported. This will gather information on what the participants found helpful and what could be improved for future studies. This questionnaire was created in collaboration and upon request of the funding source Center for Health Innovation.

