6.3 Statistical Methods

- **Baseline Data:** CDRS-R, HAM-D, and other cognitive and safety assessments will be used at screening to capture baseline data.
- **Efficacy Analysis:** As this is an uncontrolled study design, the investigators understand that any change in scores or observed improvement in symptoms may not be necessarily attributable to the treatment received. Thus, efficacy analysis will be described in this context. The investigators feel that a larger study would be indicated which may be sham controlled. Repeated measures ANOVA will be used to compare depression rating scores from each of the treatment weeks compared to baseline, as well as comparing scores between follow up visits and baseline and end of treatment weeks. Pearson's r coefficient will be used to determine correlation between, CSSR-S scores, and primary endpoints (CDRS-R & HAM-D). Descriptive statistics to identify if NSSIB is present since the subject's last visit at baseline, during the interventional period and follow ups, will be used. It is worth noting that use of ANOVA analysis has been recommended by a biostatistician, but due to a small sample size, longitudinal data will not have adequate statistical power. In addition, confidence intervals will be large and results will be uninformative regarding statistical power. This uncertainty may contribute to a future study sample size that is still too small for statistical power, but a larger sample size than this protocol.
- **Pharmacokinetic Analysis:** N/A
- **Safety Analysis:** Measurement of safety is a continuous process starting with screening. Medical review of symptoms occurs at every visit. In addition, should safety concerns related to study treatment occur, additional unscheduled safety visits can be performed. Additional assessments are done weekly during the 4-week treatment phase.
- **Personnel:** Study coordinator will complete data entry into RedCap system and oversee data management. The Principle Investigator will do oversight. A TraCS biostatistician ([name]) will complete data analysis and computations and will work with the study team throughout the duration of study activities and completion.

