Appendix B: TIME AND EVENT SCHEDULE

Time and Event Schedule	Screening	Weeks 1-4 Treatment*g					Follow up**		
Study tasks	V1 (1 wk period)	V2b ; V7, V12, V17	V3, V8, V13, V18	V4, V9, V14, V19	V5, V10, V15, V20	V6, V11, V16, V21	V22^c	V23^d	V24^d
Informed consent***	x								
CDRS-R***	x					x	x	x	x
HAM D ***	x					x	x	x	x
SCID-5***	x								
MSSE	x					x	x	x	x
Trails B	x					x	x	x	x
List Generation	x					x	x	x	x
NSSIB interview & SITBI	x					x	x	x	x
C-SSRS	x					x	x	x	x
UDS ^a	x								
Urine pregnancy test ^a	x								
Vitals (HR, RR, O ² , BP, temp, weight ^h)	x ^h	x	x	x	x	x ^h	x ^h	x ^h	x ^h
Physical exam ***	x						x	x	x
AE review ^h ***	x	x	x	x	x	x	x	x	x
Medication review ***	x	x	x	x	x	x	x	x	x
Satisfaction Questionnaire									x
Neurological exam***	x								
iTBS ^f ***		x	x	x	x	x			

Footnotes

a: Can be done anytime at investigator discretion for safety purposes, predose on any treatment day.

b: Treatment should start by the following business day, within 7 days of screening.

c: 1 week after last treatment.

d: 4 weeks after last treatment.

e: 12 weeks after last treatment.

f: First day of treatment will determine motor threshold

g: Will include change in pregnancy status (OHRE SOP 4801, re: verbal assessments for treatments w/o known teratogenic effects)

h. Weight also collected as planned timepoint – per investigator discretion can also be obtained at any time during participation

*: To be done Monday-Friday, can start any day of the week.

**: +/- 3 days

***: M.D. must be present and/or perform tasks.

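### Section 6.3 summarises NSSIB as present or absent since the last visit, a look-back that lengthens from 7 to 21 to 56 days over follow-up, so unchanged sporadic self-injury would tend to read as rising

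*Combined protocol and SAP*

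**What the plan says.** Aim 1 Hypothesis 3 (section 2.0) states: "Adolescents with MDD who demonstrate NSSIB at the start of the trial will show reduction in NSSIB after iTBS treatments". Section 6.2 lists change in NSSIB as a secondary endpoint, to be evaluated descriptively, and the synopsis adds Pearson correlations between changes in NSSIB, depression and suicidality.

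Section 6.3 defines the NSSIB summary. Descriptive statistics are to "identify if NSSIB is present since the subject's last visit at baseline, during the interventional period and follow ups". It gives no length for the look-back.

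In Appendix B the row "NSSIB interview & SITBI" is marked at screening (V1), at the fifth session of each treatment week (V6, V11, V16, V21) and at V22, V23 and V24. Treatment visits are daily on weekdays: "To be done Monday-Friday, can start any day of the week". Section 3.1 sets three follow-up appointments to "evaluate long-term efficacy and safety at 1 week, 4 weeks, and 12 weeks since the last treatment session", and Appendix B allows 3 days either side. The V24 column carries the 4-week footnote, but sections 3.1 and 4.3 both make that visit 12 weeks.

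Section 5.2 describes a second recall period for the same interview occasions: "lifetime and past month will be assessed using the Self-Injurious Thoughts and Behaviors Interview (SITBI) short form". It says the tool assesses frequency, then labels it: "This is a descriptive, yes/no assessment". Section 3.4 adds: "The presence of suicidality or NSSIB are not required to enter this study", and concedes that there may be few data.

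**The concern.** Presence since the last visit depends on two things: how often the subject self-injures, and how long ago the last visit was. The second changes by design across the follow-up schedule. A subject whose behaviour is constant is more likely to be recorded as positive at V24 than at V22 simply because eight weeks are being asked about instead of one. A reader of the table would take that as self-injury returning after treatment.

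The comparison with baseline is also undefined. Screening has no prior visit, so section 6.3 does not say what period the baseline answer covers, yet Hypothesis 3 is a comparison with baseline. During treatment, visits are daily and NSSIB interviews weekly, so the last visit can be taken as the previous day or as the previous interview. Two analysts could build different tables from the same sentence. Because the analysis is descriptive, the table is the result, and the study is meant to supply preliminary data for a larger one.

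**Working it through.** The plan gives no window length or self-injury rate, so there is no figure of its own to reproduce.

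**1. Windows from the schedule** (no unscheduled visits; V21 is the last treatment)

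- V22: 7 - 0 = 7 days; with the 3-day allowance, 4-10.
- V23: 28 - 7 = 21 days; allowance at both ends, 15-27.
- V24: 84 - 28 = 56 days; allowance at both ends, 50-62.
- The three ranges do not overlap.
- V11, V16, V21: 7 days since the previous NSSIB interview. Read literally as the previous visit, 1 day, or 3 when the fifth session falls on a Monday.
- V6: V2 to V6 spans 4 days for a Monday start and 6 otherwise. If V2 is 1-7 days after V1, the window since V1 is 5-13 days.
- V1: undefined.

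**2. Expected presence when nothing changes**

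Assume a constant rate of one episode per *m* days. The chance of at least one episode in *d* days is 1 - exp(-*d*/*m*). The rates are assumptions, shown as a range.

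| Assumed rate | V22 (7 d) | V23 (21 d) | V24 (56 d) | Fixed 30 d |
|---|---|---|---|---|
| 1 per 90 days | 7.5% | 20.8% | 46.3% | 28.3% |
| 1 per 60 days | 11.0% | 29.5% | 60.7% | 39.3% |
| 1 per 30 days | 20.8% | 50.3% | 84.5% | 63.2% |
| 1 per 15 days | 37.3% | 75.3% | 97.6% | 86.5% |
| 1 per 7 days | 63.2% | 95.0% | 100% | 98.6% |

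At one per 30 days the visit allowance gives 12-28%, 39-59% and 81-87%. If rates vary between subjects (gamma, shape *k* = 0.5, same mean), presence is 1 - (1 + *d*/(30*k*))^(-*k*), or 17%, 36% and 54%. If the rate halves after V22, presence still rises: 21%, 30% and 61%. Since 56/7 = 8, the rate would have to fall eightfold for V24 to read the same as V22.

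**3. One unchanged subject**

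- Absent at V22, present at V24: exp(-7/*m*) × (1 - exp(-56/*m*)). For the five rates in table order: 43%, 54%, 67%, 61%, 37%.
- The reverse: (1 - exp(-7/*m*)) × exp(-56/*m*), or 0-4%.
- With a subject-specific gamma rate shared by both windows, let P0(*d*) = (1 + *d*/(*mk*))^(-*k*). Absent then present is P0(7) - P0(63), or 28-39%. The reverse is P0(56) - P0(63), or 1-2%.
- For a subject with one episode per 2 days, absent then present is 3%; for a daily rate, 0.1%.

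**4. Baseline to treatment**

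Only if baseline is read as SITBI past-month presence do unequal windows create a fall: at one per 30 days, from 63% (30 days) to 21% (7 days) with no change in behaviour.

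**5. What a 30-day look-back covers**

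- V2 to V21 is 25 days for a Monday start and 27 otherwise, with no missed sessions. At V21 the look-back therefore includes 30 - 25 = 5 or 30 - 27 = 3 pre-treatment days.
- V23 at day 28 reaches back to 2 days before the last session (5 if held on day 25).
- V24 at day 84 reaches back to day 54. Days 28-54 are not covered.

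**The case against.** The strongest reply is about weight. NSSIB is exploratory, descriptive, and observed in five subjects who need not have it. Section 6.3 already warns that changes may not be due to treatment, and in so small a listing the visit dates are easy to see. That stands as a limit on importance. It does not answer the point, because the sparse-data and attribution caveats concern imprecision and the lack of a control group, not a look-back that changes length.

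The second reply is that the SITBI already supplies past-month recall at every NSSIB visit, and section 6.2 does not exclude its use. That is correct and makes the remedy cheap. But the summary that section 6.3 names is the since-last-visit one.

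The third is that this item covers follow-up without gaps, which matters because NSSIB is also a safety assessment. That stands: past-month data should be added, not substituted.

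Section 6.3 could also be read as meaning since the baseline visit. That window lengthens at every visit too, so the problem remains.

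A reader might infer that the plan builds in a false treatment benefit. The documents do not support that. The follow-up bias works against benefit, and the fall in step 4 needs a past-month baseline that section 6.3 does not specify.

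**Conclusion.** The point holds with modest weight. Followed as written, section 6.3 compares presence over windows of 7, 21 and 56 days, so unchanged sporadic self-injury tends to read as increasing over follow-up. At one episode per 30 days the expected reading is 21%, 50% and 85%. One unchanged subject reads as absent then present with probability 37-67%, against 0-4% for the reverse (28-39% against 1-2% with a gamma-distributed rate).

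The windows come from the schedule; the percentages rest on assumed rates and on a constant rate over time. The direction holds for any constant low or moderate rate and becomes negligible for a subject with no self-injury or near-daily self-injury.

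A reader might go further and say that the study's conclusions on efficacy or durability are at risk. They are not: the primary endpoint and the feasibility criteria do not use NSSIB, and Hypothesis 2, on persistence to 12 weeks, concerns depressive symptoms. What is affected is the evidence for Hypothesis 3, and the synopsis correlation if its NSSIB change is built from the same item.

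**What to change.** In section 6.3:

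- Make SITBI past-month NSSIB presence at V1, V21, V23 and V24, listed per subject, the summary used for change in NSSIB (section 6.2, Hypothesis 3 and the synopsis correlation).
- Keep the since-last-visit item at every NSSIB visit as a gap-free safety listing. Show the days since the previous NSSIB interview beside each answer, and do not compare presence across visits with different windows.
- State that the V21 past-month window includes about 3-5 pre-treatment days, and that roughly days 28-54 after treatment are covered only by the since-last-visit item.
- Show the all-subject result beside the Hypothesis 3 subgroup, noting that selecting subjects on baseline NSSIB produces some fall by itself. No percentage should be attached, since its size depends on how rates vary between subjects.

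With a fixed 30-day look-back, constant behaviour at one episode per 30 days reads a flat 63% in unselected subjects.

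The cost is SAP wording. The interview is already scheduled at these visits, and a yes/no answer is enough. The downside is two NSSIB listings, and past-month windows that overlap in places and leave gaps in others.

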6.4 Sample Size and Rationale

This is a pilot study to measure the efficacy, duration, safety and feasibility iTBS in 5 adolescents with MDD. It will not be powered to show significance. The study may provide important preliminary data for NIH (National Institute of Health) R01 applications. In addition, safety and tolerability will be documented for all 5 subjects to support the expansion of recruitment for future research. The sample size was determined by several factors. This is a novel study treatment for adolescents, thus using smaller sample size will help evaluate safety and feasibility in a safe manner. In addition, realistic logistical factors were considered: there is time commitment of treatment required, our patient pool at our clinic, and realistic ability to enroll and complete the study in a year's given time. We expect to have 5-10 patients consented, accounting for potential screen failures. We also have parents calling our clinic asking for TMS/ iTBS treatment but insurance will not cover it, so we are confident we will be able to successfully recruit. All statistical estimates of population parameters will be tabulated along with corresponding confidence intervals.

6.5 Interim Analysis

No interim analysis will be planned for this study. However, should serious or significant AE's (Adverse Events) become prevalent and at investigator discretion with a causality of likely or very likely related to iTBS, the study will be stopped for safety reasons.

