4.6 Rescue medication administration: N/A

4.7 Subject Completion / Withdrawal procedures

Subjects who complete the study will be reminded of the study team's contact information should they have any questions in the future. Files will be kept under lock and key in a locked office in a secure facility for the

required amount of time according to GCP (Good Clinical Practice) principles and FDA regulations. For those wishing to withdraw from the study early, a termination visit will be scheduled to ensure safety, proper follow up, review adverse effects, and medications. CDRS-R, HAM-D, all cognitive, and safety assessments will be performed for final data capture if the patient agrees.

Patients will be withdrawn by investigators if they miss 20% of planned treatments, for noncompliance, or any other issues the PI determines can cause harm to the patient.

We will not replace discontinued participants. We will use the data we have up until discontinuation.

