9.0 SAFETY MANAGEMENT

- Our protocol includes multiple safety assessments, which include the MMSE, Trails B, list generation, C-SSCR. In addition, we will be performing a review of systems during each visit, which will include the common adverse effects seen in the literature as described in the side-effects section. [12,24]
- **Hearing:** All subjects will be provided ear plugs to be used during the sessions.
- **Adverse Event/Serious Adverse Event monitoring procedures:** Serious and non-serious AE's will be monitored and documented at every visit. Additional referrals or follow up will be provided on an as-needed basis. See Appendix C for a copy of the UNC template AE log used for documentation.
- **Adverse Event/Serious Adverse Event reporting procedures:** UNC policy will be followed for reporting of serious and non-serious adverse events. If the event is unexpected and related or possibly related to treatment and serious or suggests new/ increased risk, this will be reported to the IRB. Reports of AE's will be made within 24 hours of investigators discovering the reportable event.
- **Medical Emergency procedures:** In the rare event of a medical emergency, the investigators performing iTBS are medically trained to handle the situation. In addition, the location of the study will operate in proximity to UNC emergency department, and 911 can be called for assistance. Investigators and study coordinator are Basic Life Support and CPR (Cardiopulmonary resuscitation) certified.
- **Data Safety Monitoring Plan:** Adverse events will be continuously monitored by investigators and assessed for severity, risk to benefit ratio, causality from study treatment. Study will be stopped if suspected pattern of lack of efficacy or additional risk of harm vs. benefit emerges.

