APPENDIX C: ADVERSE EVENT LOG

ADVERSE EVENT Make a separate entry for: ➤ All new adverse events ➤ All AEs with increased severity ➤ All AEs with changes in study drug relationship ➤ All medical conditions present at study drug initiation which have worsened	✓ if AE meets definition of serious*	Grade / Intensity Asymptomatic Mild Moderate Severe	Start Date	End Date	Relationship to study intervention Related Possibly Not Likely Not Related	Was Action Taken? (Circle One) Yes/No	Action(s) Taken^:	Outcome: Recovered Not Recovered Recovered w/Sequelae Fatal Unknown	PI Initials / Date
----------------------------------------------------------------------------------------------------------------------------------------------------------------------------------------------------------------------------------------------------------------------------	--------------------------------------------	--------------------------------------------------------------------	---------------	-------------	----------------------------------------------------------------------------------------------	------------------------------------------------	----------------------	---------------------------------------------------------------------------------------	-----------------------

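### The 6.5 stop waits for adverse events to become prevalent among five adolescents and uses causality grades the log lacks; no text requires a decision before the next subject starts

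*Combined protocol and SAP*

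**What the plan says.** Section 6.5 plans no interim analysis but provides for a safety stop "should serious or significant AE's (Adverse Events) become prevalent and at investigator discretion", "with a causality of likely or very likely related to iTBS". It gives no number of events or subjects.

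The log in Appendix C records causality under "Relationship to study intervention Related Possibly Not Likely Not Related" and ends with a sign-off column, "PI Initials / Date".

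Section 9.0 adds three things:
- Ongoing review: "Adverse events will be continuously monitored by investigators and assessed for severity, risk to benefit ratio, causality from study treatment".
- A second stop: "Study will be stopped if suspected pattern of lack of efficacy or additional risk of harm vs. benefit emerges".
- Reporting: "UNC policy will be followed for reporting of serious and non-serious adverse events". Events that are unexpected, related or possibly related to treatment, and either serious or suggestive of new or greater risk go to the IRB. The reporting time is 24 hours from discovery.

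For the individual subject, 4.2 requires a safety check before each treatment, 4.7 has the investigators withdraw a subject over issues the PI considers harmful, and 8.0 lets them remove a subject who worsens. Section 3.3 expects subjects to be treated singly, because of the daily visit schedule, and gives caution about safety in younger patients as one reason for starting with a small number.

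**The concern.** The small sample is presented partly as a safety measure (3.3, 6.4). It protects later subjects only if an early serious event leads to a decision before they begin. A rule that waits for events to become prevalent does not work that way in a group of five, and its causality condition cannot be read directly off the form on which causality is recorded.

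What is at stake is the interval between a first serious, possibly treatment-related event and the next adolescent's first session. The plan allows the investigators to stop in that interval. It does not require them to decide anything within it.

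**Working it through.** The stopping rule has no numeric threshold, so there is no plan figure to reproduce. The check is mainly a comparison of texts, with simple counts.

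**Inputs.** 5 subjects (3.3); 20 sessions each over four weeks (4.2, 7.0); treatment one at a time expected (3.3); 20% missed-session limit (4.7, 8.0); start within 7 days of screening (Appendix B, footnote b); last follow-up 12 weeks after treatment (4.3).

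**1. The frequency condition.** If one subject is affected and *k* have been treated, the observed proportion is 1/*k*: 1/1 = 100%, 1/4 = 25%, 1/5 = 20%. The same single event can be called prevalent or not according to when it occurs. The plan's only numeric limit touching side effects is in Aim 3, which accepts one withdrawal in five. That is a feasibility criterion, not a stopping rule.

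**2. The causality condition.**
- 6.5, stop: likely or very likely.
- 9.0, IRB report: related or possibly related.
- 4.4, unscheduled visit: probably related.
- Appendix C, log: Related, Possibly, Not Likely, Not Related.

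The 9.0 wording fits the log. The 6.5 wording does not, and no mapping is given. Related is the nearest grade. An event rated Possibly has a route to the IRB through 9.0 but no stated place in 6.5.

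**3. Does any safeguard fix a decision before the next subject starts?**
- 9.0, second stop: usable after one event, but its condition is a judgement and no time is set.
- 9.0, IRB reporting: has a 24-hour limit, but informs the IRB without holding anyone. The specific IRB trigger covers unexpected events. Seizure is a listed risk in section 1.0, so it might be classed as expected, although institutional policy could still require a report.
- 4.2, 4.7 and 8.0: concern the subject under treatment, not the next one.
- Appendix C sign-off: documents the event and the action taken, not whether the study proceeds.
- 3.3, treatment in turn: expected for scheduling reasons, not required as a safety interval.

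None does.

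**4. Exposure still planned.** After an event in subject *k*, (5 − *k*) × 20 sessions remain for later subjects: 80, 60, 40 and 20 for *k* = 1, 2, 3 and 4.

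**5. What a hold would run into.** The missed-session limit is 0.20 × 20 = 4 sessions, so a hold of four treatment days could reach it. Section 4.7 is mandatory ("Patients will be withdrawn by investigators if they miss 20% of planned treatments"), while 8.0 makes removal optional. Neither says whether a session withheld by the investigators counts as missed. A hold could also outlast the four-week schedule, or the 7-day start window of a subject already screened.

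**6. Calendar.** With strictly sequential treatment and each screening overlapping the previous subject's treatment, the study needs 1 + 5×4 + 12 = 33 weeks. Without overlap it needs 5×(1+4) + 12 = 37. Of 52 weeks, 19 or 15 remain for start-up (length not given), recruitment gaps and any hold.

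**The case against.** The strongest reply is that this is a missing timing sentence, not a missing safeguard. Adverse events are reviewed continuously, and subjects are checked before every session. The 9.0 stop is worded as something that will happen on merely suspected added harm. Qualifying events reach the IRB within 24 hours, including those rated only possibly related. A careful PI would probably pause anyway. The PI holds overall responsibility and initials the log, so divergent readings of causality are less likely than the wording suggests, and equating likely or very likely with Related is natural. Institutional policy, adopted by reference and not available here, may already require a pause.

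Most of this stands, and it lowers the priority. It does not supply the missing link: none of the cited text makes a recorded decision a condition for starting the next subject.

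A reader might infer that the plan would let 80 more sessions proceed after a serious event in subject 1. The documents do not support that. The 80 sessions are what remains scheduled if nobody acts, and 9.0 and 4.7 give the investigators both duty and power to act. Nor does the text define prevalent as two of five, or as any other count, so error rates calculated for such a threshold would rest on an invented rule.

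**Conclusion.** The point holds as a gap in the stated rule. Section 6.5 uses a frequency condition poorly suited to five subjects and grades absent from the log, and no section ties a first serious, possibly related event to a decision before the next subject's first session. It is a cheap safety improvement of modest priority.

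Its size is the exposure still scheduled when the decision is due: up to four subjects and 80 sessions, assuming sequential treatment and an event in subject 1. The documents do not allow a statement of how often the hold would be used. They give no rate for serious related events other than seizure, and the seizure figure in section 1.0 (0.06%, regular TMS) has no stated unit.

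It may be tempting to support the point with confidence intervals for one event in five or with seizure probabilities. Neither is needed: 6.5 is a discretionary clinical stop, and neither it nor the proposed hold uses an estimated proportion.

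**What to change.** Keep the stops in 6.5 and 9.0 and leave the decision with the PI. Then:

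- **6.5, causality:** replace likely or very likely with the log grade Related.
- **6.5, hold:** add that a seizure, or any adverse event marked serious and rated Related or Possibly, in one subject holds further iTBS in that subject and in any concurrent subject, and also the next subject's first session. The hold lasts until the PI has recorded a decision to continue, modify or stop and the IRB has been notified.
- **4.7 and 8.0:** state that held sessions are deferred and do not count as missed.
- **4.2 and 7.0:** let the four-week schedule extend by the length of the hold.
- **Appendix B, footnote b:** allow re-screening if the 7-day start window lapses.

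The cost is a short amendment to these sections, using the existing PI, log and IRB route, with no extra staff or patients. The downside is a short delay, expected to be rare, and possibly a repeat screening. Some holds will follow serious events later judged unrelated, such as a hospitalisation for depression first rated Possibly, and a waiting depressed adolescent would then start later. On the calendar above, the year has room for a short hold if start-up and recruitment gaps do not use up the 15 to 19 spare weeks.
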